1 INTRODUCTION

This Statistical Analysis Plan (SAP) describes data-handling and statistical procedures to be used for Study KD025-217 as specified in protocol (Amendment No. 1, 08 September 2021): Extended Treatment and Follow-up of Subjects Treated with Belumosudil in Study KD025-208 or Study KD025-213.

The SAP was written in accordance with the recommendations outlined in the International Conference on Harmonisation (ICH) E9 Guideline entitled "Guidance for Industry: Statistical Principles for Clinical Trials" and the most recent ICH-E3 Guideline, entitled "Guidance for Industry: Structure and Content of Clinical Study Reports."

2 STUDY SUMMARY

2.1 Study Objectives

2.1.1 Primary objective

 The objective of this study is to evaluate long-term safety and efficacy of belumosudil in subjects with Chronic Graft Versus Host Disease (cGVHD) who have previously been treated with belumosudil.

2.1.2 Secondary objectives

- Duration of Responses (DOR): Response is defined by the 2014 National Institutes of Health (NIH) Consensus Development Project on clinical trials in cGVHD and are assessed by investigators
- Change in Lee Symptom Scale Score (LSS)
- Time to Next Treatment (TTNT)
- Failure Free Survival (FFS)
- Overall Survival (OS)
- Percentage of subjects who have a best response of Partial Response (PR) and percentage of subjects who have a best response of Complete Response (CR)
- Response by individual organ
- · Change in corticosteroid dose
- Change in cGVHD Global Severity Rating based on the Clinician-reported Global cGVHD Activity Assessment

2.2 Study Design

KD025-217 is a Phase 2, open-label, extended treatment and follow-up study in subjects with cGVHD who have been previously treated with belumosudil in Study KD025-208 or in Study KD025-213.

Subjects who have signed the Informed Consent Form (ICF) will be enrolled in Study KD025-217 if they have met any of the following conditions:

- Actively receiving belumosudil in Study KD025-208 or in Study KD025-213 (excluding adults in the Companion Study and excluding adolescents enrolled under KD025-213 Amendment 2 [01June 2020])
- Is in long-term follow-up (LFTU) on Study KD025-208 or Study KD025-213. Long-term follow-up will be defined as the period after ending treatment with belumosudil and until an FFS event occurs.
- Adult enrolled in the Companion Study as specified in Study KD025-213 Amendment 2 (01 June 2020) and received at least 6 months of treatment or is in LTFU.

After signing the ICF, at Baseline, subjects will undergo efficacy assessments by Clinician-reported Global cGVHD Activity Assessment, response assessment, pulmonary function tests (PFTs), LSS score, and documentation of corticosteroid dosage and/or other therapies for cGVHD.

Subjects will undergo safety assessments including symptom-directed Physical Exams (PE), vital signs, weight, height, Karnofsky Performance Scale (KPS), hematology and clinical chemistry laboratory testing, pregnancy testing, 12-lead Electrocardiogram (ECG), documenting concomitant medications, and monitoring for Adverse Events (AEs). Subjects will continue on their same dosing regimen they received in Study KD025-208 or Study KD025-213: belumosudil 200 mg QD, 200 mg BID, or 400 mg QD. If the Investigator reduced the subject's dose of belumosudil in either Study KD025-208 or Study KD025-213, the subject will continue to receive that same reduced dose treatment with belumosudil throughout Study KD025-217 or until the AE that led to the temporary dose reduction has resolved, in which case the dose treatment can resume at the original dose at the discretion of the Investigator. Subjects will begiven a study drug diary to record daily dosing. Subjects may be administered the first dose either in the clinic or self-administered at home.

At 3 months after Baseline and every 3 months thereafter (± 14 days), subjects will report to the clinic for the same efficacy and safety assessments and dispensing of belumosudil at Baseline.

Kadmon Corporation

Page 8 of 26

(Height is only required at Baseline.) The study drug diaries for the past 3 months will be collected, and new study drug diaries dispensed. Any remaining belumosudil will be collected. Subjects may receive belumosudil on Study KD025-217 for up to an additional 2 years, at the discretion of the Investigator (and with guidance from the medical monitor), beyond what they had received in Study KD025-208 or Study KD025-213, cGVHD progression, or unacceptable toxicity.

Subjects will return to the clinic for a 28-day Follow-up Visit at 28 days (± 7 days) after the last dose of study drug. Subjects will have LFTU approximately every 3 months until an FFS event occurs. After the 28-day Follow-up Visit has been completed, subjects will be contacted approximately every 3 months by telephone, e-mail, or postal mail to confirm survival status, any initiation of new systemic cGVHD therapies, and relapse of underlying disease. Alternatively, this information may be obtained from the subject's medical records.

2.3 Visit Schedule and Study Assessment

The flow chart of visit schedule and study assessments is given in Appendix A of the KD025-217 Protocol.

3 STATISTICAL METHODS

3.1 General Methods

3.1.1 Computing Environment

All statistical analyses will be performed using SAS® Version 9.4 or higher for Windows.

3.1.2 Sample Size Justification

No formal power calculation will be performed to determine the study sample size.

3.1.3 General Considerations

General considerations for descriptive statistics, presentation, and analysis model (for efficacy analysis) used for continuous and categorical data are given below.

3.1.3.1 Reporting of Numerical Values

Continuous data will be described using descriptive statistics: number of observations (n), mean, standard deviation, median, minimum and maximum. Frequencies and percentages will be used for summarizing categorical data. When categorical data are presented, the percent will

Kadmon Corporation

Page 9 of 26

be suppressed when the count is zero in order to draw attention to the non-zero counts. The denominator for all percentages, unless otherwise specified, will be the number of subjects in the specified analysis population or group.

Means, medians, standard deviations, and confidence intervals will be reported to one decimal place more than the data reported on the case report form (CRF) or by the laboratory/vendor. Minimum and maximum will be reported to the same number of decimal places displayed on the CRF or by the laboratory/vendor. P-Values will be reported to 4 decimal places.

3.1.4 Study Day

The study day for all assessments prior to the first study drug administration is calculated as the difference between the date of the measurement (e.g., assessment date, sample collection date, etc.) and the start date of study treatment. The day before the start of study treatment is Study Day -1.

The study day for all post assessments after the first study drug administration is calculated as the difference between the date of the measurement (e.g., assessment date, sample collection date, etc.) and the start date of study treatment in parent study KD025-208/KD025-213, plus one day. The first day of study treatment is Study Day 1.

3.1.5 Baseline

Baseline value for efficacy analyses is defined as the valid and last non-missing value obtained within 28 days prior to subject receiving the first study medication in parent study KD025-208/KD025-213.

Baseline value for safety analyses is defined as the "Baseline" visit from KD025-217.

Baseline can be the day before the first study medication or on the same day as the first study medication if a pre-dose assessment is available. Subjects without data on a parameter before the first study medication will have a missing baseline for this parameter.

3.1.6 Handling of Incomplete or Missing Data

Missing data will not be imputed in general and it will be reported as missing in all listings. For categorical variables, patients with missing data are not included in calculations of percentages unless otherwise specified.

3.1.6.1 Missing start and end dates for AE and concomitant medication (CM)

The assumption will be the worst or most conservative judgment when imputing AE and CM start and end dates. The purpose of imputing a start date is to help define whether the AE/CM started while taking study drug.

For a partial or missing start date:

- If the day is missing, the first day of the month will be imputed. If the missing day is the same as the month of first dose of study drug, then the first dose date will be imputed.
- If the day and month are missing, the first day of January will be imputed. If the year is the same as the first dose date, then the first dose date will be imputed.
- If the day is completely missing, the first dose date will be imputed. If the end date suggests it could have started prior to this, the first day of January of the same year as the end date will be imputed.
- When imputing a start date, the start date will ensure that the new imputed date is sensible, i.e., is prior to the end date of the AE or CM.

For a partial or missing end date:

- If the day is missing, the last day of the month or the last assessment date, whichever is earlier, will be imputed.
- If the day and month are missing, the 31st of December or the last assessment date, whichever is earlier, will be imputed.
- If the date is completely missing, there will be a need to look at whether the AE/CM is still ongoing before imputing a date. If the ongoing flag is missing, then it will be assumed that AE is still present, or CM is still being taken (i.e., do not impute a date). If the AE/CM has stopped, then the last assessment date will be imputed.

These data imputations are for categorization purpose only and will not be used in listings.

If the assessment of the relationship of the AE to belumosudil is missing, then it will be assumed that the AE is related to belumosudil and the AE considered as such in the frequency tables of possibly related AEs. No imputation should be done at the data level.

Kadmon Corporation

Page 11 of 26

3.1.6.2 Missing event dates

Event date will be imputed only when day is missing, and the purpose of imputing an event date is to most conservatively calculate time to event. If the day is missing, the first (mid, last) day of the month will be imputed for undesired (neutral, desired) event. If the missing day is the same as the month of first dose of study drug, then the first dose date will be imputed for undesired event. These data imputations are for time to event calculation only and will not be used in the listings.

3.2 Analysis Populations

Full Analysis Set: The Full Analysis Set is defined as all subjects enrolled in the study. All safety and efficacy analyses will be performed on the Full Analysis Set.

There are 3 treatment groups for this study: belumosudil 200 mg QD, 200 mg BID, and 400 mg QD. Each subject's treatment group is determined by their originally assigned dosing cohort (Study KD025-208) or randomized arm (Study KD025-213).

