#### Efficacy Follow-up Variables

- Duration of Responses (DOR): Response is defined by the 2014
   National Institutes of Health (NIH) Consensus Development Project on clinical trials in cGVHD and are assessed by investigators
- Change in Lee Symptom Scale Score (LSS)
- Time to Next Treatment (TTNT)
- FFS
- Overall Survival (OS)

	
 
Percentage of subjects who have a best response of PR and percentage of subjects who have a best response of CR
 
		
	Response by individual organ		
	Change in corticosteroid dose		
	Change in cGVHD Global Severity Rating based on the Clinician-reported Global cGVHD Activity Assessment		
Safety Follow-up Variables	Safety assessments will be performed at regular intervals and will include AEs, Grade ≥ 3 AEs, serious adverse events (SAEs), PEs, vital sign measurements, clinical laboratory evaluations, and ECGs. Reasons for treatment discontinuation will be documented.		
	The AE reporting period for a subject enrolled in the study will begin when the subject signs the informed consent and is continued through the 28-day Follow-up Visit at 28 days (± 7 days) after their last dose study drug.		
Statistical Analysis	An interim analysis will be performed when all patients have completed at least 3 years of treatment with belumosudil or withdrew earlier (not inclusive of the companion study subjects).		
	Study Subjects Demographic (e.g., gender, age, and race) and Baseline characteristics will be summarized.		
	Efficacy Analyses: The efficacy endpoint analyses include		
	• DOR		
	Change in LSS		
	• TTNT		
	• FFS		
	• OS		
	
 
Proportion of subjects with a CR and proportion with a PR
 
		
	Response by individual organ		
	Change in corticosteroid use		
	Change in cGVHD global severity rating based on the Clinician-reported Global cGVHD Activity Assessment.		
	Safety Analyses:		
	Safety Analyses.  Safety analyses will be performed on all subjects who receive at least 1 dose of belumosudil.		

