#### 4.3 Inclusion Criteria

- 1. Subjects must have been treated with belumosudil for at least 1 of the following criteria:
  - Actively receiving belumosudil on Study KD025-208 or on Study KD025-213 (excluding adults in the Companion Study and excluding adolescents enrolled under KD025-213 Amendment 2 [01 June 2020])
  - b. Is in LTFU on Study KD025-208 or on KD025-213. Long-term Follow-up will be defined as the period after ending treatment with belumosudil and until an FFS event occurs.
  - c. Adult enrolled in the Companion Study under KD025-213 Amendment 2
     (01 June 2020) who has received at least 6 months of treatment of belumosudil or is in long-term follow-up
- 2. Female subjects of childbearing potential have a negative pregnancy test at enrollment. Females of childbearing potential are defined as sexually mature females without prior hysterectomy or who have had any evidence of menses in the past 12 months. However, females who have been amenorrheic for 12 or more months are still considered to be of childbearing potential if the amenorrhea is possibly due to prior chemotherapy, anti-estrogens, or ovarian suppression.
- 3. Sexually active females of childbearing potential enrolled in the study must agree to use 2 forms of accepted methods of contraception during the course of the study and for 3 months after their last dose of study drug. Effective birth control includes:
  - a. Intrauterine device plus 1 barrier method
  - Stable doses of hormonal contraception for at least 3 months (e.g., oral, injectable, implant, transdermal) plus 1 barrier method

- 2 barrier methods. Effective barrier methods are male or female condoms, diaphragms, and spermicides (creams or gels that contain a chemical to kill sperm) or
- d. A vasectomized partner
- 4. For male subjects who are sexually active and who are partners of females of childbearing potential: agreement to use 2 forms of contraception and to not donate sperm during the treatment period and for at least 3 months after the last dose of study drug.
- Subject (or the subject's legally authorized representative) is able to provide written informed consent prior to the performance of any study-specific procedures.
- 6. It is in the best interest of the subject to participate in the study.

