#### 9.3 Analysis Populations

The populations for efficacy and safety analyses will be the Full Analysis Set consisting of all subjects enrolled in the study.

There are 3 treatment groups for this study: belumosudil 200 mg QD, 200 mg BID, and 400 mg QD. Each subject's treatment group is determined by their originally assigned dosing cohort (Study KD025-208) or randomized arm (Study KD025-213).

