### 9.9 Safety Analyses

Safety analyses will be performed on all subjects who receive at least one dose of belumosudil.

Adverse events will be coded using the Medical Dictionary of Regulatory Activities (MedDRA) (Version 24.0 or greater). The number and percentages of subjects experiencing TEAEs will be tabulated by System Organ Class and Preferred Term (PT). The number of events by PT will also be summarized. Tabulation by maximum severity and relationship to treatment will also be included by treatment group.

Summary subject listing will be provided for SAEs, AEs resulting in study discontinuation, and deaths.

Adverse events, SAEs, related AEs, related SAEs, Grade  $\geq$  3 AEs, related Grade  $\geq$  3 AEs, and AEs leading to withdrawal and treatment discontinuation, and deaths will be summarized.

Laboratory results will be summarized by treatment group, incidence of laboratory abnormalities, and worst on-study grade during the treatment period will be summarized. The incidence of Grade  $\geq$  3 laboratory abnormalities under treatment and shifts in toxicity grading from Baseline to highest grade post-baseline will be displayed.

Vital sign measurements and ECGs will be summarized by treatment group at each scheduled time point using descriptive statistics and included in data listings.

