3.3 Subject Disposition and Evaluability

A disposition of safety population, the number of subjects discontinuing from treatment, and the primary reason for discontinuation will be summarized. This summary will also be presented by exposure range.

Subject listing will be provided for the disposition of subjects who died during study.

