3.8 Safety Analysis

Safety assessments include AEs, clinical laboratory evaluations (hematology and chemistry), vital sign measurements, and electrocardiograms. Unscheduled visits for safety assessments will not be presented in by visit summary tables but will be in listings and shift tables. All safety analyses will be performed using the safety population.

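### The safety set is described in three ways, and on the all-enrolled set any subjects who enter in long-term follow-up would dilute the KD025-217 adverse event percentages

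*SAP*

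**What the plan says.** **The set for safety analyses**

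- SAP 3.2 defines only the Full Analysis Set (all enrolled) and adds: "All safety and efficacy analyses will be performed on the Full Analysis Set".
- Protocol 9.3 agrees: "The populations for efficacy and safety analyses will be the Full Analysis Set consisting of all subjects enrolled in the study".
- SAP 3.8 says: "All safety analyses will be performed using the safety population". SAP 3.3 uses the same undefined term: "A disposition of safety population, the number of subjects discontinuing from treatment, and the primary reason for discontinuation will be summarized".
- Protocol 9.9 says: "Safety analyses will be performed on all subjects who receive at least one dose of belumosudil". The synopsis repeats this: "Safety analyses will be performed on all subjects who receive at least 1 dose of belumosudil". Neither says in which study the dose must be taken.

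**Who enrols.** Protocol 4.3 admits subjects on drug in a parent study and subjects in LTFU who have stopped drug and had no failure-free survival (FFS) event. Protocol 6.2.2 and the notes to Appendix A limit subjects who enter in LTFU to a contact about every 3 months. Under Protocol 6.2.5 that contact covers survival, new systemic cGVHD therapy and relapse.

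**The periods covered.** SAP 3.8.1 opens the treatment-emergent window at the first administration of study medication, without naming the study, and closes it 28 days after end of treatment. SAP 3.6 measures exposure from an equally unnamed first dose, in bands that end with one above 36 months.

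**The concern.** Long-term safety is half of the study's single objective, and AE percentages by dose group are its main summary. Two programmers working from this text could use different sets. If they follow SAP 3.2, every subject who enters in LTFU joins the denominator of the KD025-217 AE tables with almost no chance of contributing an event. The printed percentages would then describe a mixture of treated and untreated subjects. If the LTFU share differs between dose groups, so does the dilution, and a side-by-side reading of the 200 mg QD, 200 mg BID and 400 mg QD columns is affected.

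The second gap concerns time rather than subjects. If exposure runs from the parent-study first dose while AEs are counted only from KD025-217 consent, the patient-years and the event counts do not belong together.

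**Working it through.** **1. Can a subject who enters in LTFU contribute a treatment-emergent AE to a KD025-217 table?**

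- Dosing: such subjects have permanently stopped belumosudil (Protocol 6.2.5).
- Collection: AE collection runs from consent to 28 days after the last dose (Protocol 6.4 and Appendix A). For these subjects the last dose was in the parent study, so the period has normally ended before consent. The exception is a subject who stopped less than 28 days earlier.
- Window: if SAP 3.8.1 means the first KD025-217 dose, the window never opens. If it means the parent first dose, it has normally closed.
- Denominator: SAP 3.1.3.1 divides by the number in the analysis population. Having no AE record is a non-event, not a missing value, so the missing-data rule in SAP 3.1.6 does not remove these subjects.

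They therefore count as event-free.

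**2. Size of the dilution.** The plan gives no AE rate or LTFU count for KD025-217, so there is no figure to reproduce. Let N be the number enrolled, L the number entering in LTFU, and x the number of dosed subjects with the event.

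- Dosed set: p = x/(N-L).
- All enrolled: x/N = p × (N-L)/N.

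N = 70 is the approximate enrolment in Protocol 4.1. L and p are assumptions.

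| L | (N-L)/N | p = 20% prints as | p = 40% prints as |
|---|---|---|---|
| 0 | 70/70 = 1.00 | 20% | 40% |
| 7 | 63/70 = 0.90 | 18% | 36% |
| 14 | 56/70 = 0.80 | 16% | 32% |
| 21 | 49/70 = 0.70 | 14% | 28% |

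The same factor applies within each dose group, using that group's own N and L. Protocol 5.2 shows that the 400 mg QD group comes only from KD025-208 while the other two draw on both parents, so equal factors cannot be presumed.

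**3. Do AE counts and exposure cover the same period?**

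- Passages about AEs and safety point to KD025-217: reporting starts at consent (Protocol 6.4), recording covers events after consent (Protocol 7.2), and only ongoing AEs are carried over from the parent study (Protocol 6.2.2). SAP 3.1.5 says "Baseline value for safety analyses is defined as the" KD025-217 Baseline visit.
- Exposure points to cumulative data: KD025-217 allows up to 2 further years (Protocol 3.1), yet three of the seven bands in SAP 3.6 lie above 24 months. They would be essentially empty unless parent-study dosing counts. SAP 3.1.4 also counts study day from the parent first dose once dosing has begun.

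Followed as written, the SAP could pair cumulative patient-years with KD025-217 events. It plans no exposure-adjusted AE rate, so the mismatch would enter through a reader's own comparison of the two tables.

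**The case against.** The strongest reply is that the denominator is settled on a literal reading. Both sections headed Analysis Populations name the Full Analysis Set. The at-least-one-dose wording selects the same people, because Protocol 4.3 begins: "Subjects must have been treated with belumosudil for at least 1 of the following criteria". A smaller set appears only if the reader adds a requirement for dosing in KD025-217 that no passage states. On that view, *safety population* is a stray synonym, and replacing it with Full Analysis Set would make the text consistent.

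The textual part of this stands. It does not dispose of the point, because the consistent all-enrolled reading is the one that counts subjects entering in LTFU as event-free in KD025-217 tables.

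Three stronger readings are tempting, and the documents do not support them:

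- A reader might infer that the silence on pooling parent-study AEs leaves the denominator open. Pooling changes the numerator, the window and the patient-years; the number of subjects in the Full Analysis Set stays the same.
- A reader might infer that the text is evenly split on pooling. The AE-specific passages lean to KD025-217 only. Those that look cumulative concern exposure, study day and the interim trigger (3 years of treatment, Protocol 9.6), and can coexist with KD025-217-only AE tables.
- A reader might infer a large L from Protocol 1.4.1 and 1.4.2, where 37 - 7 = 30 and 119 - 70 = 49 subjects were off drug but still followed at 19 February 2020. That date is more than 18 months before the protocol amendment the SAP cites (8 September 2021), and those counts are not restricted to subjects without an FFS event, as LTFU entry is. They show that an off-drug pool existed, not how many would enrol.

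**Conclusion.** The point holds in a conditional form. The naming inconsistency is certain. The dilution by (N-L)/N arises if AE tables count KD025-217 events only and L is above 0; at L = 0 there is none, and if parent-study AEs are pooled most of it disappears. The percentages in the table are illustrations, not forecasts. The possible mismatch between AE counts and patient-years follows from the text, but its size cannot be computed from the documents.

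The consequence is descriptive. Protocol 9.1 sets no formal hypothesis, and no test or decision rule depends on these percentages. Laboratory and ECG means are unaffected because subjects without values do not enter them, and SAP 3.1.6 already excludes missing data from categorical percentages. SAEs, AEs leading to discontinuation and deaths are still listed by subject. This should be corrected before the safety tables are programmed, but it does not threaten the study.

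**What to change.** 1. In SAP 3.2, define the safety population as enrolled subjects with at least one dose of belumosudil in KD025-217. Remove safety from the Full Analysis Set sentence, and use the new set for KD025-217 AE and other safety tables in SAP 3.8.
2. In SAP 3.8.1 and 3.6, name the study whose first dose starts the treatment-emergent window and the exposure period, and make the two match. For any cumulative table that includes parent-study data, use all enrolled subjects; a set dosed in KD025-217 would select those who stayed on drug.
3. In SAP 3.3, keep disposition on all enrolled subjects, split into dosed in KD025-217 and LTFU-only. This also puts L on record.
4. Align Protocol 9.3, Protocol 9.9 and the synopsis at the next amendment.

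Items 1 to 3 are SAP wording and a few extra table splits, with no new data collection. Item 4 needs IRB/IEC submission under Protocol 13, so it can wait for an amendment made for other reasons. AE percentages may be higher than on the all-enrolled set. Deaths among LTFU-only subjects need no separate table: overall survival on the Full Analysis Set and the death listings already cover them.
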